Once the SP is deemed eligible and is consented, an in-person enrollment visit will be scheduled with the patient. After the patient has read the consent form, they can request to take time to consider the information and schedule a 2nd visit to complete enrollment if they choose. During the informed consent process the RA will ask the patient questions to make sure they understand what is involved with the study. The patient will be allowed to think about sections in the consent and take time to digest the information. If they choose not to enroll at that time, they will be asked whether the team can contact them again if they have a newly-qualifying HbA1c at a later date. If the patient feels comfortable with what was presented to them in the consent and they are still interested in enrolling, the patient will be asked to sign the consent form, and a copy will be given to them for their records. If the patient consents to participate, a baseline survey and physiologic measurements (blood pressure, weight, fingerstick HbA1c).

² Only one family member will be able to enroll in the study as a SP for tracking and assessment purposes.

Randomization

Once both the patient and SP complete all of these steps, they will be randomized into one of the two study arms: FAM-ACT or I-DSMES.

ELIGIBILITY CRITERIA

INCLUSION CRITERIA

FQHC Adult Patient with Diabetes:

- Have a diagnosis of diabetes in the FQHC EMR Problem List (ICD10 codes E08.xx, E09.xx, E11.xx, E13.xx, O24.1x, O24.3x, O24.8x, O24.9x)
- Most recent HbA1c, done in the 3 months prior to screening phone call $\geq 7.5\%$
- If A1c not ≥ 7.5 , can also qualify due to poor blood pressure control, defined as: Systolic BP >139 mm Hg in the FQHC EMR (ECW) official vital sign field (not in note text etc) two or more times in the last 6 months, with the most recent SBP also being >139 mm Hg
- Are 21 or over, and less than 75 years old, at the date of screening phone call
- Plan to use FQHC for health care over the next 12 months (after enrollment)
- Must be able to identify a family member or friend who is involved in their health care and willing to be contacted about participating in the study with the patient

Support Person:

- Expects to be able to attend intervention sessions in person if invited
- Must be at least 21 years old

EXCLUSION CRITERIA

FQHC Adult Patient with Diabetes:

- Was diagnosed with diabetes at age <21 years

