1. Take part in a one-hour introductory session designed to provide an overview of diabetes complications, how to set goals, and prepare for/participate in primary care appointments. During this session, the patient's diabetes complication risk profile will be discussed.
2. Be invited to 4-6 group diabetes self-management education sessions to be held at the FQHC or online using Pitt's HIPAA-compliant Zoom environment. In-person sessions at the FQHC will last approximately 1.5 hours whereas online sessions will be designed to last approximately 45 minutes. American Diabetes Association-approved 'Conversation Maps' will be used as a tool for patient education when feasible.
3. Complete an additional survey assessment and lab measures (blood pressure, weight and fingerstick blood HbA1c) with the study RA 6-months after enrollment. The SP will only complete one additional survey assessment 6 months after enrollment⁴. (*Some patients in both arms may be contacted 12-15 months post-enrollment to complete an additional assessment if the study still is active at the time that assessment window opens.*)
4. Receive care management contacts with a CHW every 2-4 weeks either in person or remotely (when necessary). The CHW will talk with the patient for approximately 20 minutes each time for the remainder of the 6-month enrollment period.
5. Patients who enrolled in the study prior to August 2020 will be contacted by phone for an additional, optional "FAM-ACT COVID" survey. The purpose of this survey is to determine how the events of the COVID-19 pandemic have affected patients' ability to participate in the intervention, and to care for their diabetes

PROGRAM B: SP-FOCUSED DSMES (FAM-ACT)

The FAM-ACT intervention will include patients and their SP together as much as possible. In this arm, the enrolled FQHC Patient and their SP (referred to as a dyad) will:

1. Take part in a one-hour introductory session designed to provide an overview of diabetes complications, ways the SP and patient can work together positively, and ways to set "SMART" health goals. During this session, results of a diabetes complication risk profile are discussed with the patient and support person and the dyad learns how to set goals together.

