2. Be invited to 4-6 family-focused, group diabetes self-management education sessions to be held at the FQHC or online using Pitt's HIPAA-compliant Zoom environment. In-person sessions at FQHC will last approximately 2 hours each, whereas online sessions will be designed to last approximately 1 hour. American Diabetes Association-approved "Conversation Maps" will be used as a tool for providing patient education when

⁴ In both arms, a +3 month assessment window will be permitted for both patient and SP assessments.

feasible. Additional family-focused topics will be discussed, such as patient-SP communication and SP roles in helping patients participate actively in healthcare provider appointments.

3. Complete additional survey assessments and lab measures (blood pressure, weight, fingerstick A1c, and lipids) with the study RA 6-months after enrollment. The SP will only complete one additional survey assessment 6-months after enrollment.
4. Receive care management contacts with a CHW every 2-4 weeks either in person or remotely (when necessary). The CHW will talk with the dyad for approximately 20 minutes each time for the remainder of the 6-month enrollment period.
5. Patients who enrolled in prior to August 2020 will be contacted by phone for an additional, optional "FAM-ACT COVID" survey. The purpose of this survey is to determine how the events of the COVID-19 pandemic have affected participants' ability to participate in the intervention, and to care for their diabetes

Additionally, the patient will have their FQHC electronic chart reviewed for diabetes-related visit, lab, and medication information for the period from 12 months prior to 24 months following their study enrollment date.

INTERVENTION PROCEDURES CONDUCTED IN BOTH STUDY ARMS

A trained and supervised CHW, CHW Manager, and/or RA at the FQHC will conduct all research participant contacts. Contacts at the FQHC will be supervised by the CHW Manager and Site PI. In-person diabetes self-management education group sessions will take place in a large conference room with other FQHC patients present. Online group sessions will be attended by study participants and the CHW(s). A study RA also may be present to assist with technical issues. Participant assessments will be completed in a private location at the FQHC or remotely via phone/video call or Zoom.

STUDY MEASURES

PATIENT MEASURES

Hemoglobin A1c (HbA1c)

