Secondary outcomes: The original analysis plan included 6-month and 12-month change in patient UKPDS score as a secondary outcome. The calculation of UKPDS score is based on HbA1c, SBP, cholesterol levels, and smoking status.	Secondary outcomes: Change in UKPDS score has been dropped as a secondary outcome because patient cholesterol cannot be measured reliably without in-person assessment. A substantial number of first wave patients became eligible for their 6-month assessment while restrictions on in-person research activities were in effect.
SAMPLE SIZE	
See analysis plan	
DATA COLLECTION	
HbA1c: Per the original protocol, patients were to have their HbA1c assessed at 3 time points: baseline, 5 to 7 months post-baseline and 11 to 13 months post-baseline. All assessments were to be conducted by study RAs using the fingerstick method described above.	HbA1c: To accommodate pandemic-related restrictions on in-person research activities, 2 additional HbA1c assessment methods have been incorporated into the protocol. Clinic measures. Tests unable to be obtained in-person during the assessment window will be recorded from patients' EMRs rather than obtained via a study staff-conducted assessment. Home testing. Patients may be offered the option to self-test their HbA1c using a fingerstick device (e.g. A1cNow® Self Check, pts Diagnostics) sent to their home.
Survey assessments: As part of the original protocol, SPs were to be assessed by survey at 2 timepoints: baseline and 11-13 months post-baseline.	Survey assessments: Because the duration of the study protocol was decreased from 12 to 6 months, SPs now will be surveyed at baseline and 6-9 months post-baseline.

CHW, community health worker; DSMES, diabetes self-management education and support; EMR, electronic medical record; FAM-ACT, Family Support for Health Action; FQHC, Federally Qualified Health Center; HbA1c, hemoglobin A1c; I-DSMES, individual patient-focused diabetes self-management education and support; SBP, systolic blood pressure; SP, support person; UKPDS, UK Prospective Diabetes Study

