2.0 STUDY OBJECTIVES

FAM-ACT aims to compare the effectiveness of a family supporter-focused (FAM-ACT) intervention relative to an individual patient-focused diabetes self-management education and support (I-DSMES). Specifically:

1. Determine the effectiveness of FAM-ACT, compared to I-DSMES, in improving patients' diabetes-related health outcomes (primary: Hemoglobin A1c [HbA1c]; secondary: blood pressure)
2. Determine the effectiveness of FAM-ACT, compared to I-DSMES, in improving patients' health behaviors and perceived support
3. Examine theoretical-model-driven moderators and mediators of FAM-ACT participation on patient outcomes

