3.2 BLINDING

All assessments will be conducted by blinded research associates. Due to the nature of the intervention, participants, their SPs, and care providers cannot be blinded.

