4.0 STUDY ENDPOINTS AND COVARIATES

4.1 PRIMARY ENDPOINT

The primary outcome is the change in patient glycemic control from baseline to 6 months. Glycemic control is measured by HbA1c in %.

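### The 6-month measurement list names lipids for FAM-ACT only; the item has no planned use and, followed literally, requires the assessor to know the arm

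*Protocol*

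**What the plan says.** The protocol states that it describes the procedures in use since February 2021, so its arm descriptions are current instructions.

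- **Program B (FAM-ACT), item 3:** "Complete additional survey assessments and lab measures (blood pressure, weight, fingerstick A1c, and lipids) with the study RA 6-months after enrollment".
- **Program A (I-DSMES), item 3:** "Complete an additional survey assessment and lab measures (blood pressure, weight and fingerstick blood HbA1c) with the study RA 6-months after enrollment".
- **Patient informed consent and enrollment (baseline, before randomization):** "a baseline survey and physiologic measurements (blood pressure, weight, fingerstick HbA1c", with nothing further in the list.
- **Appendix 1, Outcomes:** change in the UKPDS score, which used cholesterol, is no longer a secondary outcome because "patient cholesterol cannot be measured reliably without in-person assessment".
- **SAP 2.0:** the health outcomes are "primary: Hemoglobin A1c [HbA1c]; secondary: blood pressure".
- **SAP 4.1:** "The primary outcome is the change in patient glycemic control from baseline to 6 months", so the primary endpoint falls at the visit where the lists differ.
- **SAP 3.2:** "All assessments will be conducted by blinded research associates".

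**The concern.** Two arms of a randomized comparison should have the same outcome assessment. Here the list given to the research assistant at the 6-month visit depends on the arm. An assistant who follows both lists cannot know whether to collect lipids without knowing the allocation, yet the SAP says that assessors are blinded.

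The exposure matters most for the surveys. Under the protocol's heading on health behaviors and psychosocial determinants, the research assistant reads the questions aloud and records the answers. Those surveys supply most of the secondary endpoints in SAP 4.2. HbA1c is an assay result and leaves little room for assessor influence.

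The lipid item also serves no purpose in the current plan. Patients in one arm would have an extra test that enters no planned analysis.

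**Working it through.** The plan gives no figure on this point. The check is a comparison of text, followed by a ceiling on the number of visits affected.

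**1. Measurement lists side by side**

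| Place | BP | Weight | HbA1c | Lipids |
|---|---|---|---|---|
| Baseline, both arms | yes | yes | yes | no |
| 6 months, I-DSMES | yes | yes | yes | no |
| 6 months, FAM-ACT | yes | yes | yes | **yes** |

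The only difference is lipids in FAM-ACT at 6 months.

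**2. Search for a use of the lipid value**

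- Study Measures describes no lipid method. Its fallback for visits that cannot be held in person covers HbA1c, blood pressure and weight only.
- The blood-test risks listed in the protocol concern fingersticks for HbA1c only.
- SAP 4.1 and 4.2 contain no lipid endpoint. The SAP 5.2 model adjusts for baseline HbA1c, whether patient and support person live together, insulin use and age, and not for lipids.
- The complication risk profile is discussed at the introductory session, so a 6-month lipid value cannot feed it.
- The UKPDS score was the only outcome built on cholesterol, and Appendix 1 removes it.

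No use was found. From the study-visit measures listed, a lipid change cannot be formed in FAM-ACT (no baseline value), and the arms cannot be compared (no I-DSMES value).

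**3. Conflict with blinding**

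The two 6-month items both assign the measurements to the study research assistant. The lists differ only by arm, so choosing the right one requires the allocation. This conflicts directly with SAP 3.2.

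**4. Ceiling on the visits affected**

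Inputs: 268 dyads and 20% attrition (SAP 3.1); 77 dyads enrolled before March 2020 under the original protocol, and the adapted protocol in effect from February 2021 (Protocol, COVID-19 adaptations).

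- A dyad enrolled at the end of February 2020 reached 6 months at the end of August 2020. Even with the +3-month window this ends in November 2020, before the present text applied. The 77 are therefore removed.
- Dyads under the present text, assuming that the 77 count toward 268: 268 − 77 = 191.
- Expected at 6 months: 191 × 0.80 = 152.8, about 153 patients over both arms. Both arms count, because the absence of the test is as informative as its presence.
- If the 77 did not count toward 268, the ceiling would be 268 × 0.80 = 214.4, about 214.

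Either number is an upper limit. Visits where HbA1c comes from the medical record or a home test, or where the assessment is remote, involve no panel run in person by the assistant. The documents do not say how many these are.

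**The case against.** The strongest reply is that this is residual wording. Cholesterol belonged to the dropped UKPDS outcome, no lipid method survives, and one word in a narrative list does not show that any lipid test is done. That is plausible, and the documents do not settle it. It lowers the likely consequence but leaves the instruction in the current text.

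Several stronger readings are tempting and should not be drawn:

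- **That the visit form discloses the allocation.** No arm-specific 6-month form is described. The section on data collection and form development says that forms are generated by visit number. What stands is that the list, if followed, requires knowledge of the arm.
- **That blinding is impossible because of this item.** Some assessments bypass the panel. There are also other exposures: research assistants may help at online group sessions, and Appendix 1 has them mail materials to FAM-ACT support persons who live apart from the patient.
- **That no lipid change could ever be obtained.** Chart review covers diabetes-related laboratory data in both arms from 12 months before to 24 months after enrollment. The first 77 dyads enrolled while a cholesterol-based outcome was still planned. Either source might hold lipid values, but the protocol names none and plans no analysis of them.
- **That cholesterol cannot be measured reliably at all.** Appendix 1 says this only of assessment that is not in person.
- **That a lipid result in one arm could prompt extra care.** The privacy sections bar sharing assessment information with clinicians unless the patient appears to be in danger, and the planned alert values are for blood pressure and symptoms.

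**Conclusion.** The point holds as an inconsistency in the current protocol and a conflict with the SAP's blinding statement. The 6-month lists differ by arm, the extra item has no planned use, and following it requires knowledge of the allocation.

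The consequence is moderate. It bears mainly on the survey outcomes and only on visits where the research assistant runs the panel in person. The ceiling is about 153 patients, assuming that the 77 original-protocol dyads are part of the 268 and that attrition is 20%. The true number could be far lower, and is zero if the wording is residual and no lipids are collected. No planned analysis, sample size or power figure changes. A reader might infer that the primary HbA1c comparison is biased; the documents do not support that.

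**What to change.** In Program B item 3, delete the two words that add lipids to the list. Both arms then have the same 6-month panel (blood pressure, weight, fingerstick HbA1c), which also matches baseline. Confirm that the working visit forms and research assistant instructions carry no lipid item for either arm.

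The cost is a two-word edit and that check. If the test is being done, the edit saves it; no planned analysis is lost. The change removes one threat to assessor blinding. It does not deal with research assistants attending online sessions or mailing FAM-ACT materials, so it does not by itself make the statement in SAP 3.2 secure.

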It will be made clear to participants that no information gathered through study assessments will be shared with participants' clinicians unless the patient appears to be in danger (in cases of suicidality, for example) and [name] (PI) or [name] (Site-PI) deems it necessary to contact the participant's physician. Electronic assessment data and analytic files will be maintained on secure servers that are protected in accordance with the University of Pittsburgh data security requirements. Only approved research personnel will have access to study files. Research data will be presented in aggregate statistics only. Throughout the study, IRB and HIPAA guidelines will be followed to ensure the privacy and integrity of the information we collect. All study personnel will complete training in maintaining patient confidentiality and will sign a written statement indicating that they will preserve the confidentiality of patient records as a condition of their employment. Any breach of confidentiality will be immediately reported to the PI and to the IRBs. In addition, any complaints or concerns expressed to the study staff by participants, providers, or anyone else affected by this study will be immediately reported to the PI and to the IRBs.

All surveys and interviews will be conducted in-person or from a private office with a closed door. To minimize the risk of loss of confidentiality, there will be no personally identifying data on survey assessments. Paper copies of all consent forms will be kept in a locked filing cabinet at the FQHC. We will create a secure electronic tracking file that maps the subject's identifying information to the arbitrary study identifier, which will serve as the participant's primary identifier for all analytic files. Survey assessments will be conducted in person for all patients and responses will be entered into the database thru tablets as the interview is being conducted. The SP surveys may be done over the telephone or in-person, depending on the SP's needs. All survey assessments will be available on paper as a backup in case electronic systems are not accessible or need to be completed over the telephone. If a paper survey assessment is used, it will contain the participant's study ID but no identifying information, and be stored in a locked filing cabinet until the data is double entered into the electronic study database.

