Alternatives: Patients may choose not to take steps that will lower their sugar or blood pressure levels. Precautions: Patients will be advised to make small changes in their self-care regimens over time and not large changes at once. They will also be advised to discuss any changes in medication regimen or physical activity routines with their healthcare providers before proceeding. All those participating in intervention sessions will be trained on how to recognize common symptoms of hypoglycemia and hypotension, and how to self-treat minor episodes. We expect that SPs in Program B (Family-Focused) will become more skilled at recognizing and managing hypoglycemia and hypotension. Safeguards: Participants will be advised to notify their healthcare providers if experiencing these effects more than once, and they will be advised to seek emergency care for severe symptoms.

Hyperglycemia or hypertension

Alternatives: Patients may choose not to take steps that increase their sugar or blood pressure levels. Precautions: Patients will be advised to make small changes in their self-care regimens over time and not large changes at once. They will also be advised to discuss any changes in medication regimen or physical activity routines with their site healthcare providers before proceeding. All those participating in intervention sessions will be trained on how to recognize common symptoms of hyperglycemia and hypertension and how to self-treat minor episodes. We expect that SPs (FAM-ACT) will become more skilled at recognizing and managing hyperglycemia and hypertension. Safeguards: Participants will be advised to notify their health care providers if experiencing these effects more than once, and they will be advised to seek emergency care for severe symptoms.

Steps that will be taken in the event that a clinically significant, unexpected disease or condition is identified during the conduct of the study include the following.

- The study Principal Investigator ([name]), Pittsburgh Project Coordinator, FQHC Site PI ([name]), and the FQHC Site Coordinator/CHW Manager will be notified.
- FQHC patients will be referred to their healthcare provider at their local site, or to emergency medical services, if appropriate. FQHC study staff will offer to directly contact the participant's local healthcare providers with the patient's permission.
- SPs will be advised to contact their own healthcare provider, or referred to emergency medical services if appropriate.

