- Eligibility confirmation: The FQHC RA, FQHC CHW, or FQHC Site Coordinator will review all screening-related CRFs and confirm eligibility with electronic signature prior to randomization.
- Consent monitoring: the clinical site will be able to upload signed participant consents to a secure repository, where the CCDC coordinator will be able to monitor them in real time.
- Complete ascertainment of primary and key secondary outcomes: The CCDC coordinator will be notified in real time if there are instances of missing outcomes, which will allow the coordinator to query the clinical site and resolve the issue.
- Serious adverse events and protocol violations: The CCDC coordinator is notified of all SAEs and protocol violations as they occur.

The FQHC clinic Site Coordinator will be able to upload source data to the study website, where a CCDC coordinator will be able to complete a full review of source data verification of critical elements as well as regulatory documents; and participant informed consents. At the conclusion of the audit, a summary of the site visit findings will be discussed with the PI, the Site PI and study personnel. A detailed summary report will document the audit findings and can be supplied to the Study Investigators, NIDDK program staff, and the study personnel. This information will also be kept in the electronic regulatory management system.

Protocol alerts

In addition, the CCDC will work with the clinical team to define “protocol alerts” for the study. This would include email notifications for the following situations: a participant meeting enrollment criteria, a form or set of forms that need to be electronically signed by the Site PI, submission of SAEs, submission of protocol deviations, and other safety issues such as death. In addition, alert values for blood pressures and symptoms will be established. The study staff will notify the Site Coordinator, the subject, and, for FQHC patients the subject’s physician whenever there are results outside of these values because of the clinical implications of a value substantially out of normal range. Outstanding protocol alerts will be reviewed on a monthly basis with the PI.

Serious adverse events

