4.2 SECONDARY ENDPOINTS

Secondary outcome measures include the following:

- Change in HbA1c from baseline to 12 months
- Change in blood pressure from baseline to 6 months and to 12 months
 - Blood pressure will be measured by an automatic blood pressure monitor, taking the average of two readings taken 2 minutes apart. We will average the SBP at 6 months and 12 months and compare to SBP at baseline.
- Change from baseline to 6 months and to 12 months in diabetes distress in patient and in SP
 - The Problem Areas in Diabetes (PAID-5) Scale is comprised of 5 closed-ended items with response options ranging from 0 ('not a problem') to 4 ('serious problem'). The scale's 5 items will be summed to create a total score with a range of 0 to 20. A total score of ≥ 8 indicates possible diabetes-related emotional distress that warrants further assessment, with higher scores suggesting greater diabetes-related emotional distress.
- Change from baseline to 6 months in diabetes self-care behaviors in patient - including domains of diet, exercise, blood sugar testing, blood pressure checking, foot care and medication taking.
 - The Summary of Diabetes Self-Care Activities (SDSCA) is a brief self-report instrument for measuring levels of self-management across different domains of the diabetes regimen. Our study will score results within each domain by averaging the item scores (each ranging from 0-7) within each domain.
- Change from baseline to 6 months in self-efficacy of patient and of SP
 - The Self-Efficacy for Managing Chronic Diseases Scale is comprised of 5 items asking respondents to indicate how confident they are that they regularly can perform tasks related to their diabetes management. Responses range from 0 to 10, with higher numbers indicating greater self-efficacy.
- Change from baseline to 6 months in patient activation
 - The Patient Activation Measure (PAM)-10 uses a 4-point scale (1=strongly disagree to 4=strongly agree), where respondents indicate the extent to which statements related to being ready, willing and able to manage their health and health care accurately describe them. Responses are summed to create a total score with higher numbers indicating greater activation.
- Patient perceived overall satisfaction with SP support for diabetes from baseline to 6 months

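### The protocol orders staff to notify a patient's physician of every alert-level blood pressure or symptom result, yet promises participants no such sharing unless the patient appears in danger and a PI agrees

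*Protocol*

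**What the plan says.** Three parts of the protocol deal with passing study findings to a patient's own clinician.

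- **Data & Safety Monitoring, *Protocol alerts*.** The protocol states that "alert values for blood pressures and symptoms will be established". It continues: "The study staff will notify the Site Coordinator, the subject, and, for FQHC patients the" patient's "physician whenever there are results outside of these values because of the clinical implications of a value substantially out of normal range". Outstanding alerts are then reviewed monthly with the PI.
- ***Privacy and confidentiality* (under risk minimisation), repeated almost word for word in *Participant Privacy*.** "It will be made clear to participants that no information gathered through study assessments will be shared with" their "clinicians unless the patient appears to be in danger (in cases of suicidality, for example) and [name] (PI) or [name] (Site-PI) deems it necessary" to make contact. Both sections also require any confidentiality breach to be reported at once to the PI and to the ethics boards.
- **Steps for an unexpected, clinically important disease or condition (end of the risk-minimisation text).** The PI, Site PI and coordinators are told, and the patient is referred to a provider or to emergency services if appropriate. In addition, "FQHC study staff will offer to directly contact the" patient's local providers, subject to the patient's permission.

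**The concern.** A blood pressure or symptom report obtained at a study assessment falls under both the alert rule and the privacy promise. The alert rule makes physician notification automatic. The promise forbids it unless two conditions are met together. Neither text refers to the other.

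Two things are at stake. The first is safety handling: staff who keep the promise hold back a result that the alert text itself regards as clinically important. The second is what participants are told: staff who follow the alert rule do something participants were assured would not happen. On a plain reading that could itself count as a breach reportable to the PI and the ethics boards.

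**Working it through.** No arithmetic applies; the check is a comparison of texts.

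| | *Protocol alerts* | *Privacy and confidentiality* / *Participant Privacy* | Unexpected disease or condition |
|---|---|---|---|
| Trigger | Blood pressure or symptom result outside an alert value | Any information from a study assessment | A clinically important condition that was not expected |
| Danger test | None | Required | None |
| PI or Site-PI decision | None | Required | None (they are informed) |
| Patient permission | None | Not mentioned | Required for direct contact by staff |
| Physician told | Always | Only if both conditions hold | Only with permission |
| Others told | Patient and Site Coordinator | Not restricted | PI, Site PI, coordinators; patient referred to care |

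The first two rules can then be applied to an alert-level result measured by study staff.

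1. *The patient appears in danger and a PI judges contact necessary.* Both rules lead to physician contact. No conflict.
2. *The patient appears in danger, but no PI decision has been made yet.* The alert rule orders contact; the promise bars it until the decision. Following the promise means delay.
3. *The patient appears in danger, but the PI or Site-PI does not judge contact necessary.* The alert rule orders contact; the promise bars it.
4. *The patient does not appear in danger, for example with an out-of-range pressure and no symptoms.* The alert rule orders contact; the promise bars it whatever a PI thinks.

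The two rules agree only in case 1. Treating every alert value as a sign of danger would remove case 4 but not cases 2 and 3, because the alert text contains no PI decision before the physician is told. Its stated PI step for outstanding alerts is the monthly review.

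The third rule has a different trigger and meets the alert rule only when an alert-level result also counts as an unexpected, clinically important condition. In that overlap, a patient who refuses permission produces a conflict with the alert rule. A patient who gives permission without appearing in danger produces one with the promise, which has no permission exception.

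The scope is limited to blood pressures and symptoms. HbA1c is not named among the results with alert values.

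**The case against.** The strongest reply is that this is a minimal-risk behavioural study, that the alert text looks forward (alerts are still to be defined and the monitoring plan formalised), and that an alert is never left without a response. The last part stands: the patient and the Site Coordinator are told under the alert rule, the privacy text restricts neither, and the unexpected-condition text refers patients to care where it applies. A reader might infer that an alert value could go unacted on, or that the alert procedure is the only route to the clinician. The documents support neither inference. Only direct physician notification is in doubt, and the protocol names other routes to the clinician.

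It is also fair that the permission step should not be counted as a third incompatible rule for every out-of-range result, since its trigger differs. Some study pressures may be taken from the clinic record (*Systolic blood pressure*), so the clinic already holds them. The consent pages are not in the reviewed copy, and an alert exception may appear there.

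None of this removes the contradiction. Setting the alert values later will not supply the missing PI decision. An exception in the consent form would still leave the protocol's two privacy statements at odds with its alert instruction.

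**Conclusion.** The contradiction between *Protocol alerts* and the two privacy sections is real and unreconciled. It applies to any study-obtained blood pressure or symptom result that is outside an alert value and does not meet both the danger and the PI condition. The permission step is a partial overlap. The primary outcome and its analysis are not affected.

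How many results are affected cannot be stated, because the alert values are not set and no alert rate is given. Three further readings are tempting but unsupported:

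- Multiplying 268 patients by two scheduled assessments gives 536. That counts assessments, not conflicts, and ignores attrition and pressures taken from the clinic record.
- The eligibility list admits some patients with systolic pressure above 139 mm Hg, which might suggest frequent alerts. An entry threshold is not an alert value, and Appendix 1 says the blood pressure criterion was dropped.
- SAP 4.2 says a PAID-5 total of 8 or more "indicates possible diabetes-related emotional distress that warrants further assessment". That interprets a score within an endpoint definition. It orders no notification, so it does not conflict with the alert text.

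The conclusion rests on one reading: that a blood pressure or symptom report taken by study staff is information gathered through a study assessment. The protocol's descriptions of its assessments support this.

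**What to change.** Reconcile *Protocol alerts*, *Privacy and confidentiality* and *Participant Privacy*, together with the unexpected-condition steps where they overlap, into one notification rule. It should state the trigger, who decides, who is told, and whether the patient's permission is needed, in the same terms wherever the subject comes up. Align the participant information with that rule. Which rule governs, and where the alert values lie, is for the sponsor to decide.

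The cost is a protocol wording amendment with IRB review. If the outcome changes what participants were promised, those already enrolled may need notice; the first 77 dyads joined before March 2020. The text change itself needs no new assessments.
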